2.3. Safety Run-in Cohort 3 and Phase 2 Cohort 3 (Post-Chemo Maint Mag+CC-486)

Primary, secondary, CCI objectives and endpoints for patients with newly diagnosed AML who are in CR or CRi with MRD positivity following intensive chemotherapy are as follows:

Primary Objectives	Primary Endpoints
 To evaluate the efficacy of magrolimab in combination with anti-leukemia therapy CC-486 as determined by the MRD negative CR rate (Phase 2 Cohort 3) To evaluate the safety and tolerability, and to determine the RP2D of magrolimab in combination with the anti-leukemia therapy CC-486 (Safety Runin Cohort 3) 	 MRD negative CR rate, defined as the proportion of patients who maintain CR as determined by the investigator based on prespecified criteria and reach MRD negative disease status as determined using multiparameter flow cytometry with a sensitivity of < 0.1% (Phase 2 Cohort 3) Incidence of DLTs, treatment-emergent AEs, and laboratory abnormalities according to the NCI CTCAE Version 5.0 (Safety Run-in Cohort 3)
Secondary Objectives	Secondary Endpoints
 To evaluate additional measures of efficacy of magrolimab in combination with the anti-leukemia therapy CC-486 To evaluate the safety and tolerability of magrolimab in combination with the anti-leukemia therapy CC-486 (Phase 2 Cohort 3) To evaluate the PK of magrolimab in combination with the anti-leukemia therapy CC-486 To evaluate the immunogenicity of magrolimab in combination with the anti-leukemia therapy CC-486 	 MRD negative CR/CRi rate RFS OS Duration of MRD negative CR Duration of MRD negative CR/CRi RBC transfusion independence rate Platelet transfusion independence rate Incidence of treatment-emergent AEs and laboratory abnormalities according to the NCI CTCAE Version 5.0 (Phase 2 Cohort 3) Magrolimab concentrations over time Rate and magnitude of anti-magrolimab antibodies

3. STUDY DESIGN

3.1. Study Design

This is a Phase 2, open-label, multicenter, multi-arm study to evaluate magnolimab in combination with anti-leukemia therapies in patients with AML. This trial includes safety run-in cohorts (Section 3.1.1) and Phase 2 cohorts (Section 3.1.2).

The study schematic is presented in Figure 4.

Figure 4. Study Schema

Cohort 1*: 1L Unfit AML Mag+Ven+Aza: Phase 2 Safety run-in (N=6) Safety Previously untreated AML evaluation and Magrolimab + venetoclax RP2D Magrolimab + patients age ≥ 75 years or + azacitidine venetoclax + azacitidine ineligible for intensive N = 40induction chemotherapy Cohort 2: R/R AML Mag+MEC: Safety run-in (N=6) Phase 2 Safety AML patients who are evaluation and Magrolimab + MEC refractory, in first, or in RP2D Magrolimab + MEC second relapse after N=30 intensive induction chemotherapy Cohort 3*: Post-chemo Maint Mag+CC-486: Phase 2 Safety run-in (N=6) Safety evaluation and AML patients in CR or CRi Magrolimab + CC-486 RP2D with intensive induction Magrolimab + CC-486 chemotherapy who are N = 40MRD+

AML = acute myeloid leukemia; MEC = mitoxantrone, etoposide, and cytarabine; MRD = minimal residual disease; RP2D = recommended Phase 2 dose

st Cohorts 1 and 3 closed to enrollment globally as of Protocol Amendment 5.

3.1.1. Safety Run-in Cohorts

This study will include the following 3 safety run-in cohorts:

- Safety Run-in Cohort 1 (1L Unfit AML Mag+Ven+Aza), closed to enrollment globally as of Protocol Amendment 5: magrolimab + venetoclax + azacitidine in patients with newly diagnosed, previously untreated AML who are ineligible for intensive chemotherapy
- Safety Run-in Cohort 2 (R/R AML Mag+MEC): magrolimab + MEC in patients with R/R AML
- Safety Run-in Cohort 3 (Post-chemo Maint Mag+CC-486), closed to enrollment globally as of Protocol Amendment 5: magrolimab + CC-486 as maintenance therapy in patients with newly diagnosed AML who are in CR or CRi with MRD positivity following intensive chemotherapy

Initially, 6 patients will be enrolled into Safety Run-in Cohorts 1, 2, and 3 to receive study treatment according to the dose levels presented in Table 1, Table 2, or Table 3, respectively. A DLT assessment period of 1 cycle (28 days) will occur. The DLT assessment period and definition are provided in Sections 3.1.1.1 and 3.1.1.2.

Dose de-escalation decisions will be made as follows:

- If no more than 2 patients in a safety run-in cohort experience a DLT in Cycle 1, enrollment into the corresponding Phase 2 cohort will begin at this dose level.
- If 3 or more (> 33%) patients in a safety run-in cohort experience a DLT up to the end of Cycle 1, another 6 patients will be enrolled in that cohort at a lower dose and evaluated in the same manner to define the RP2D.

De-escalation dose levels for each safety run-in cohort are presented in Table 4, Table 5, and Table 6. Any dose de-escalation for Cohorts 1 and 3 will occur with the combination regimen, as there is a lack of dose-dependent toxicities observed with magrolimab in over 500 patients treated to date with magrolimab as monotherapy or in combination, and agents being evaluated in combination with magrolimab have identified or potential dose-related toxicities as cytotoxic agents (ie, venetoclax and CC-486). For Cohort 2, any dose de-escalation will occur with magrolimab, as the combination with chemotherapy (ie, MEC) has not been extensively studied. The selected RP2D for any cohort cannot exceed the identified MTD for that cohort.

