3.1.1.1. DLT Assessment Period

The DLT assessment period is the first cycle (28 days). For patients who are being evaluated for prolonged myelosuppression (Section 3.1.1.2), the 28-day DLT assessment period will extend to 42 days for Safety Run-in Cohorts 1 and 2. Patients are considered evaluable for assessment of a DLT if either of the following criteria is met in the DLT assessment period:

- The patient experienced a DLT at any time after initiation of the first dose of study treatment.
- The patient did not experience a DLT and completed at least 4 infusions of magrolimab and at least 14 doses of venetoclax and 5 doses of azacitidine (Safety Run-in Cohort 1), at least 3 days of dosing with MEC (Safety Run-in Cohort 2), or at least 10 doses of CC-486 (Safety Run-in Cohort 3).

If a patient experiences a DLT during the DLT assessment period, the investigator should contact the medical monitor to discuss whether the patient can remain on study drug.

Patients who are not evaluable for DLT will be replaced in the safety run-in cohorts.

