3.1.1.2. DLT Definition

All toxicities will be graded according to the NCI CTCAE Version 5.0. A DLT is defined as any Grade 4 or higher hematologic toxicity or Grade 3 or higher nonhematologic toxicity (that has worsened in severity from pretreatment baseline) during the 4-week DLT assessment period and is related to magrolimab or magrolimab combination.

The following are exceptions to the DLT definition and are NOT considered DLTs:

- Myelosuppression (Grade 4 neutropenia and thrombocytopenia) lasting no longer than 42 days from the start of study treatment for Cohorts 1 and 2, and no longer than 21 days from the start of study treatment for Cohort 3. Complications within the first 4 weeks that are associated with myelosuppression, such as fevers, infections, bleeding, and related hospitalizations, will also not be considered DLTs. However, Grade 4 neutropenia or thrombocytopenia lasting longer than 42 days from the start of study treatment for Cohorts 1 and 2, or 21 days from the start of study treatment for Cohort 3, without evidence of leukemia, will be considered DLTs. Absence of residual disease must be verified by peripheral blood count and bone marrow aspirate and biopsy at Day 43 (+ 10 days) for Cohorts 1 and 2.
- Grade 3 indirect/unconjugated hyperbilirubinemia that resolves to ≤ Grade 2 or pretreatment baseline with supportive care within 7 days and is not associated with other clinically significant consequences.
- Grade 3 isolated electrolyte laboratory abnormalities that resolve to ≤ Grade 2 or pretreatment baseline with supportive care within 7 days and are not associated with other clinically significant consequences.

- Grade 3 elevation in alanine aminotransferase (ALT), aspartate aminotransferase (AST), or alkaline phosphatase (ALP) that resolves to ≤ Grade 2 or pretreatment baseline with supportive care within 7 days and is not associated with other clinically significant consequences.
- Grade 3 nausea, vomiting, or diarrhea that resolves to ≤ Grade 2 or pretreatment baseline with supportive care within 7 days.
- Grade 3 fatigue that resolves to ≤ Grade 2 or pretreatment baseline within 2 weeks.
- Grade 3 magrolimab IRRs in the absence of an optimal pretreatment regimen, which is defined as acetaminophen or a comparable non-steroidal anti-inflammatory agent, plus an antihistamine and corticosteroids.

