- Other single laboratory values out of normal range that have no clinical correlate and resolve to Grade ≤ 2 or to pretreatment baseline within 7 days with adequate medical management.
- Transient Grade 3 nausea, vomiting, diarrhea, local reactions, influenza-like symptoms, myalgia, fever, headache, acute pain, or skin toxicity that resolves to ≤ Grade 2 within ≤ 72 hours after medical management (eg, supportive care, including immunosuppressant treatment) has been initiated.
- Grade 3 or 4 TLS or related electrolyte disturbances (hyperkalemia, hypophosphatemia, hyperuricemia) that resolve to ≤ Grade 2 within 14 days.

The recommended dose for the Phase 2 cohorts will be determined by the sponsor based on all relevant clinical and PK data from all patients treated in the safety run-in cohorts.

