8.3.1.2. Safety

The primary analysis set for safety analyses is the Safety Analysis Set. It includes all patients who receive at least 1 dose of study treatment, with treatment assignments designated according to the actual treatment received. This analysis set will be used in the analyses of safety endpoints, as well as study treatment administration. All data collected during treatment up to 70 days (± 7 days) after treatment discontinuation will be included in the safety summaries.

The DLT Evaluable Analysis Set includes all patients in the Safety Analysis Set who are enrolled in the safety run-in cohorts, have safety assessments through the protocol-specified DLT assessment window (first 4 weeks of study dosing, inclusive), and fulfill the criteria for evaluation for DLT specified in Section 3.1.1.

Safety assessments relevant to the DLT Evaluable Analysis Set definition include laboratory serum chemistry tests and hematology tests as specified in Section 3.1.1. The RP2D will be based on the DLT Evaluable Analysis Set.

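### The Cohort 2 run-in gate is worded to a 28-day Cycle 1, but the protocol's own prolonged-cytopenia DLT cannot be called before Day 43; the DLT windows in Sections 3.1.1, 3.3 and 8.3.1.2 need aligning with Section 3.1.1.2

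*Protocol*

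**What the plan says.** **Gate (Protocol 3.1.1, repeated in the synopsis).** Phase 2 enrollment starts if 2 or fewer run-in patients "experience a DLT in Cycle 1, enrollment into the corresponding Phase 2 cohort will begin at this dose level". If 3 or more "experience a DLT up to the end of Cycle 1, another 6 patients will be enrolled in that cohort at a lower dose". The same section says "A DLT assessment period of 1 cycle (28 days) will occur", and points to 3.1.1.1 and 3.1.1.2 for the period and the definition. Section 3.3 also has run-in patients evaluated for DLTs after one 28-day cycle.

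**Period (3.1.1.1).** For patients being evaluated for prolonged myelosuppression, "the 28-day DLT assessment period will extend to 42 days for Safety Run-in Cohorts 1 and 2".

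**Definition (3.1.1.2).** The general definition refers to a 4-week period. Grade 4 neutropenia and thrombocytopenia of up to 42 days in Cohorts 1 and 2 are excepted. But "Grade 4 neutropenia or thrombocytopenia lasting longer than 42 days from the start of study treatment for Cohorts 1 and 2", without evidence of leukemia, is a DLT. That no leukemia remains "must be verified by peripheral blood count and bone marrow aspirate and biopsy at Day 43 (+ 10 days) for Cohorts 1 and 2".

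**Analysis set (8.3.1.2).** The DLT Evaluable Analysis Set uses the "DLT assessment window (first 4 weeks of study dosing, inclusive", with no mention of the extension, and the RP2D is based on that set.

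**The concern.** The gate is the only cohort-level DLT count the protocol prints before 30 further Cohort 2 patients, and possibly 5 to 10 more, are enrolled (3.1.2). Its wording closes the count at Day 28. One type of DLT that the protocol itself defines cannot be called by then.

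That DLT matters here. Because shorter episodes are excepted, outlasting 42 days is the only way Grade 4 neutropenia or thrombocytopenia becomes a DLT in Cohort 2. MEC is myelosuppressive (5.3.6), severe neutropenia is reported with magrolimab (7.8.1.3), and 3.1.1 says the combination has not been studied extensively. Prolonged marrow suppression is therefore a central question for this run-in, and the literal gate leaves it out.

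**Working it through.** The protocol gives no operating characteristics for the gate, so there is no stated figure to reproduce. The 83.1% power in 8.10 is not involved and does not change.

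**Step 1. The windows side by side (Cohort 2).**

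| Section | Last day covered |
|---|---|
| 3.1.1 gate bullets, synopsis | Day 28 |
| 3.3, evaluation after one cycle | Day 28 |
| 3.1.1.2, general definition | 4 weeks |
| 8.3.1.2, analysis set | 4 weeks |
| 3.1.1.1, extended period | Day 42 |
| 3.1.1.2, cytopenia DLT and its verification | Day 43 to Day 53 (43 + 10) |

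The DLT becomes callable 43 − 28 = 15 days after the gate closes, and at the latest 53 − 28 = 25 days after. It falls 43 − 42 = 1 day beyond even the extended period. In Cohort 3 the corresponding limit is 21 days, which fits inside 28, so the shared gate wording works there and fails for Cohorts 1 and 2. Cohort 2 is the one still open.

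**Step 2. A worked case.** Two patients have a DLT by Day 28. A third still has Grade 4 neutropenia at Day 43 with a leukemia-free marrow. The literal gate and 8.3.1.2 count 2 of 6 and open Phase 2. The definition in 3.1.1.2 counts 3 of 6, and the dose drops. Of the 28 possible pairs (early DLTs, late cytopenia DLTs) in 6 patients, 12 split the two counts in this way, for example 2 + 1, 1 + 2 and 0 + 3. That is a count of patterns and not a probability.

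**Step 3. Illustration under assumed rates.** Let q be the chance of a DLT by Day 28, and r the added chance that a patient's first DLT is late cytopenia. Neither is in the documents. With 6 evaluable patients the gate passes if X ≤ 2, where

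P(X ≤ 2; p) = (1−p)^6 + 6p(1−p)^5 + 15p²(1−p)^4.

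At p = 0.20 this is 0.262 + 0.393 + 0.246 = 0.901. The other values needed are 0.984 (p = 0.10), 0.953 (0.15), 0.831 (0.25), 0.744 (0.30), 0.647 (0.35), 0.544 (0.40) and 0.344 (0.50).

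The full count is never below the 28-day count, so P(pass at Day 28, fail on the full count) = P(X ≤ 2; q) − P(X ≤ 2; q + r). Differences are taken before rounding.

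| q | r = 0.05 | r = 0.10 | r = 0.20 |
|---|---|---|---|
| 0.10 | 0.031 | 0.083 | 0.240 |
| 0.20 | 0.071 | 0.157 | 0.357 |
| 0.30 | 0.097 | 0.200 | 0.401 |

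At r = 0 the two counts always agree.

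**Step 4. The schedule.** Appendix Table 3 places the Cycle 1 marrow at Day 28 with a window of ± 1 week, so Day 35 at the latest. The Day 43 marrow required by 3.1.1.2 is not listed there.

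**The case against.** The strongest reply is that 3.1.1 should be read with the subsections it cites. It sends the reader to 3.1.1.1 and 3.1.1.2 for the period and the definition, and a specific 42-day rule would have no purpose if the gate ignored it. Watching through Day 42 and verifying at Day 43 is a coherent sequence. Grade 4 cytopenia that starts after MEC in Cycle 1 could be called a Cycle 1 event by its onset. MEC is held in a leukemia-free patient with severe cytopenia (5.3.6) and a cycle starts with MEC (5.3), so Cycle 1 may in practice run long. Phase 2 opens only after the run-in is complete and the RP2D identified (3.1.2), and the sponsor sets the dose "based on all relevant clinical and PK data from all patients treated in the safety run-in cohorts".

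Much of this stands. It shows that late cytopenia was meant to count and that the sponsor is free to wait. A reader might infer that the protocol commands opposite actions on one result, or that Phase 2 was or will be opened on an incomplete count. The documents support neither.

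Two further inferences also fail. The bases for the RP2D in 3.1.1.2 and 8.3.1.2 can be read together: one names the evidence the sponsor weighs, the other the set for the DLT evaluation. Nor do blood counts stop at about Day 42, since 6.4 requires weekly counts until recovery in cytopenic patients.

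What the reply does not do is repair the text. No sentence makes the gate wait for the Day 43 result, 3.1.1.1 equates the first cycle with 28 days, 8.3.1.2 says 4 weeks, and the extension itself ends too early.

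**Conclusion.** The point holds as a misalignment in a safety decision rule that should be corrected. The intent to count late cytopenia is visible, but the gate, Section 3.3 and Section 8.3.1.2 do not carry it out, and the 42-day extension stops one day short of the event it is there to capture. Taken literally, the rule can open Phase 2 at a dose that fails the protocol's own definition.

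The firm part is the dates: a gap of 15 to 25 days between the gate's cut-off and the point at which the DLT can be called. The disagreement probabilities, 3% to 40% over the grid shown, rest wholly on assumed rates and on a strict 28-day count being applied. They show that the gap can matter and do not estimate how often it would. Sample size and power are unaffected.

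**What to change.** 1. In 3.1.1 and the synopsis, replace both references to Cycle 1 in the gate bullets with *in the DLT assessment period (Section 3.1.1.1)*.
2. In 3.1.1.1, run the extension for patients under evaluation for prolonged myelosuppression through the Day 43 (+ 10 days) verification. State that Phase 2 does not open while pending cases could bring the count to 3.
3. Use the same window in the general definition in 3.1.1.2, in 3.3 and in 8.3.1.2.
4. In Appendix Table 3, cross-reference the Day 43 marrow for those patients only.
5. If the Cohort 2 run-in is already complete, state which count was used.

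Cost: wording and one conditional cross-reference. There is no new procedure, because 3.1.1.2 already requires the Day 43 blood count and marrow. Phase 2 would wait 15 to 25 days past Day 28 only when DLTs so far number 2 or fewer and DLTs plus pending cytopenia cases reach 3 or more.

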3.1.1.1. DLT Assessment Period

The DLT assessment period is the first cycle (28 days). For patients who are being evaluated for prolonged myelosuppression (Section 3.1.1.2), the 28-day DLT assessment period will extend to 42 days for Safety Run-in Cohorts 1 and 2. Patients are considered evaluable for assessment of a DLT if either of the following criteria is met in the DLT assessment period:

- The patient experienced a DLT at any time after initiation of the first dose of study treatment.
- The patient did not experience a DLT and completed at least 4 infusions of magrolimab and at least 14 doses of venetoclax and 5 doses of azacitidine (Safety Run-in Cohort 1), at least 3 days of dosing with MEC (Safety Run-in Cohort 2), or at least 10 doses of CC-486 (Safety Run-in Cohort 3).

If a patient experiences a DLT during the DLT assessment period, the investigator should contact the medical monitor to discuss whether the patient can remain on study drug.

Patients who are not evaluable for DLT will be replaced in the safety run-in cohorts.

3.1.1.2. DLT Definition

All toxicities will be graded according to the NCI CTCAE Version 5.0. A DLT is defined as any Grade 4 or higher hematologic toxicity or Grade 3 or higher nonhematologic toxicity (that has worsened in severity from pretreatment baseline) during the 4-week DLT assessment period and is related to magrolimab or magrolimab combination.

The following are exceptions to the DLT definition and are NOT considered DLTs:

- Myelosuppression (Grade 4 neutropenia and thrombocytopenia) lasting no longer than 42 days from the start of study treatment for Cohorts 1 and 2, and no longer than 21 days from the start of study treatment for Cohort 3. Complications within the first 4 weeks that are associated with myelosuppression, such as fevers, infections, bleeding, and related hospitalizations, will also not be considered DLTs. However, Grade 4 neutropenia or thrombocytopenia lasting longer than 42 days from the start of study treatment for Cohorts 1 and 2, or 21 days from the start of study treatment for Cohort 3, without evidence of leukemia, will be considered DLTs. Absence of residual disease must be verified by peripheral blood count and bone marrow aspirate and biopsy at Day 43 (+ 10 days) for Cohorts 1 and 2.
- Grade 3 indirect/unconjugated hyperbilirubinemia that resolves to ≤ Grade 2 or pretreatment baseline with supportive care within 7 days and is not associated with other clinically significant consequences.
- Grade 3 isolated electrolyte laboratory abnormalities that resolve to ≤ Grade 2 or pretreatment baseline with supportive care within 7 days and are not associated with other clinically significant consequences.

- Grade 3 elevation in alanine aminotransferase (ALT), aspartate aminotransferase (AST), or alkaline phosphatase (ALP) that resolves to ≤ Grade 2 or pretreatment baseline with supportive care within 7 days and is not associated with other clinically significant consequences.
- Grade 3 nausea, vomiting, or diarrhea that resolves to ≤ Grade 2 or pretreatment baseline with supportive care within 7 days.
- Grade 3 fatigue that resolves to ≤ Grade 2 or pretreatment baseline within 2 weeks.
- Grade 3 magrolimab IRRs in the absence of an optimal pretreatment regimen, which is defined as acetaminophen or a comparable non-steroidal anti-inflammatory agent, plus an antihistamine and corticosteroids.
- Other single laboratory values out of normal range that have no clinical correlate and resolve to Grade ≤ 2 or to pretreatment baseline within 7 days with adequate medical management.
- Transient Grade 3 nausea, vomiting, diarrhea, local reactions, influenza-like symptoms, myalgia, fever, headache, acute pain, or skin toxicity that resolves to ≤ Grade 2 within ≤ 72 hours after medical management (eg, supportive care, including immunosuppressant treatment) has been initiated.
- Grade 3 or 4 TLS or related electrolyte disturbances (hyperkalemia, hypophosphatemia, hyperuricemia) that resolve to ≤ Grade 2 within 14 days.

The recommended dose for the Phase 2 cohorts will be determined by the sponsor based on all relevant clinical and PK data from all patients treated in the safety run-in cohorts.

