For all cohorts, specific safety assessments to monitor for expected toxicities to each of these agents will be implemented, including monitoring for anemia, myelosuppression, tumor lysis syndrome (TLS), hepatotoxicity, IRRs, and other expected toxicities.

During a pandemic, additional potential risks to patients have been identified and may include adequate study drug availability, interruptions to the study visit schedule, and adherence to protocol-specified safety monitoring or laboratory assessments. Refer to Appendix 3 for further details on the risks and risk mitigation strategy. Given the risk mitigation measures that are being implemented, the expected benefit-risk assessment to patients remains unchanged.

In summary, based on strong scientific rationale, nonclinical and emerging clinical efficacy data, and manageable safety profile with the proposed magrolimab combination regimens, this study has an acceptable risk:benefit ratio for patients who participate.

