Venetoclax should be administered orally once daily with a meal and water, at approximately the same time each day. Patients should be advised to swallow the tablet whole, and not chew, crush, or break the tablets. If a dose is missed and it has been less than 8 hours, patients should be advised to take their dose as soon as possible. If a dose is missed and more than 8 hours has passed, the missed dose should be skipped, and the next dose should be taken at the usual time. If a patient vomits after taking venetoclax, an extra dose should not be taken but rather the next dose should be taken at the usual time.

Patients treated with venetoclax may develop TLS. Assess blood chemistry (potassium, uric acid, phosphorous, calcium, and creatinine). Correct pre-existing abnormalities prior to initiation of treatment with venetoclax. Blood chemistry must be monitored for TLS at predose, 6 to 8 hours after each new dose during ramp-up (Days 1, 2, and 3), and 24 hours after reaching the maintenance dose.

For patients taking concomitant CYP3A and P-glycoprotein (P-gp) inhibitors, refer to Table 11 for venetoclax dosing and administration.

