6.5.8. Laboratory Assessments

Laboratory assessments to be performed at screening are presented in Table 13. Laboratory assessments to be performed during the study are presented in Table 14.

Table 13. Laboratory Analyte Listing (to Be Performed at Screening)

Safety Laboratory Measurements			
Chemistry (Serum or Plasma)	Hematology	Urinalysis	Other Laboratory Measurements
Sodium	Hemoglobin	RBC	Serum pregnancy test
Potassium Chloride	Hematocrit Platelets	Protein	Extended RBC phenotyping or genotyping
Bicarbonate Total protein	WBC differential ANC		Type and screen (ABO/Rh), DAT Blast evaluation (on CBC)
Albumin Calcium	Eosinophils Basophils		Bone marrow aspirate and biopsy:
Magnesium	Lymphocytes		MRD assessment Cytogenetics
Phosphorus Glucose	Monocytes Reticulocytes PT		Receptor occupancy (to be collected at selected study sites)
BUN or urea Creatinine	INR		Correlative studies
Uric acid Total bilirubin Direct bilirubin Indirect bilirubin Haptoglobin LDH AST (SGOT) ALT (SGPT)	aPTT or PTT		Peripheral blood smear: Blasts (with bone marrow assessments)
Alkaline phosphatase			

ABO = any of the 4 blood groups A, B, AB, and O composing the ABO system; ALT = alanine aminotransferase; ANC = absolute neutrophil count; aPTT = activated partial thromboplastin time; AST = aspartate aminotransferase; BUN = blood urea nitrogen; CBC = complete blood count; DAT = direct antiglobulin test; INR = international normalized ratio; LDH = lactate dehydrogenase; MRD = minimal residual disease; PT = prothrombin time; PTT = partial thromboplastin time; RBC = red blood cell; Rh = Rhesus factor; SGOT = serum glutamic oxaloacetic transaminase; SGPT = serum glutamic pyruvic transaminase; WBC = white blood cell Refer to Appendix Table 1 for collection time points.

Table 14. Laboratory Analyte Listing (to Be Performed During the Study)

Safety Laboratory	Measurements	
Chemistry (Serum or Plasma)	Hematology ^a	Other Laboratory Measurements
Sodium	Hemoglobin	Serum or urine pregnancy test
Potassium	Hematocrit	Pharmacokinetics
Calcium	Platelets	Antidrug antibodies
Chloride	WBC differential	Blast evaluation (on CBC)
Bicarbonate	ANC	
Albumin	Lymphocytes	Bone marrow aspirate and biopsy:
Glucose	Reticulocytes	MRD assessment
BUN or urea		Cytogenetics
Creatinine Uric acid (Cohorts 1 and 2)		Receptor occupancy (to be collected at selected study sites)
Phosphorus (Cohorts 1 and 2)		Correlative studies
Total bilirubin		
Direct bilirubin		Peripheral blood smear:

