- p Peripheral blood smears for general morphology will be collected predose and assessed locally.

Appendix Table 3. MEC Administration and Associated Assessment Schedule – Treatment Period (Cohort 2)

								C	ycle (28-day	y Cycl	es)						
					MEC	Cycl	le 1				MEC	Cycle	2 (and	d 3 if applic	able)a	Starting at the en	nd of MEC Cycle
Visit Window (Days)b	No	one				Ⅎ	± 3						±	3		±	3
Cycle Day	1	2	4	8	11	15	22	28	Weekly for 2 weeks ¹	1	8	15	22	28	Weekly for 2 weeks ¹	Every 4 weeks thereafter (up to 12 months of total treatment)	Every 8 weeks x 2 and every 12 weeks thereafter (up to 12 months of total treatment)
Safety																	
Pregnancy test ^c							E	very 4	weeks follo	wing (Cycle 1	Day 1				X	
CBC with differential, platelets, reticulocytes ^d	X	X	X	X	X	X	X	X	X	X	X	X	X	X	X	X	
Haptoglobin and LDH ^d	X	X	X	X						X							
Peripheral blood smear for general morphology ^{d,n}	X	X			X												
Serum or plasma chemistry ^d	X	X	X	X		X	X			X		X				X	
Vital signs ^e	X	X		X		X	X			X	X	X	X			X	
Weight	X									X						X	
Symptom-directed physical examination ^d	X			X		X				X						X	
Adverse eventsf	_																•
Concomitant medications ^f	_																-
Efficacy/ Biomarkers																	
Peripheral blood smear for blasts ^m								X						X (Cycle 2 only)			X
Peripheral blood sample for correlative studies ^g	X			X				X		X				X (Cycle 2 only)			16 weeks after end of MEC cycle

								C	ycle (28-day	Cycle	es)						
					MEC	C Cycl	le 1				MEC	Cycle	2 (and	l 3 if applic	able) ^a	Starting at the en	nd of MEC Cycle
Visit Window (Days) ^b	No	one				4	± 3						± 3	3		±	3
Cycle Day Rone marrow	1	2	4	8	11	15	22	28	Weekly for 2 weeks ^l	1	8	15	22	28	Weekly for 2 weeks ^l	Every 4 weeks thereafter (up to 12 months of total treatment)	Every 8 weeks x 2 and every 12 weeks thereafter (up to 12 months of total treatment)
Bone marrow aspirate/biopsy for correlative studies ⁱ and receptor occupancy ^h								X						X (Cycle 2 only)			X
Bone marrow aspirate/biopsy for response assessment, cytogenetics, and MRD assessment								X						X (Cycle 2 only)			X
Bone marrow slides or blocks for central review								X						X (Cycle 2 only)			X
Buccal swab ^k	X																

CBC = complete blood count; LDH = lactate dehydrogenase; MEC = mitoxantrone, etoposide, cytarabine; MRD = minimal residual disease

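### The tumor lysis exception in the DLT definition names low phosphate where high phosphate is evidently meant: a minor one-word error with a narrow effect

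*Protocol*

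**What the plan says.** Section 3.1.1.2 makes a related nonhematologic toxicity of Grade 3 or higher a DLT if it has worsened from baseline and arises in the assessment period. It then gives a list introduced by "The following are exceptions to the DLT definition and are NOT considered DLTs". Three entries bear on phosphate:

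- The tumor lysis entry: "Grade 3 or 4 TLS or related electrolyte disturbances (hyperkalemia, hypophosphatemia, hyperuricemia) that resolve to ≤ Grade 2 within 14 days".
- The isolated electrolyte entry: "Grade 3 isolated electrolyte laboratory abnormalities that resolve to ≤ Grade 2 or pretreatment baseline with supportive care within 7 days", provided there are no other clinically significant consequences.
- The single laboratory value entry: "Other single laboratory values out of normal range that have no clinical correlate and resolve to Grade ≤ 2" or to baseline, again within 7 days.

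Section 8.1.2 makes the incidence of DLTs, as defined in Section 3.1.1.2, part of the primary endpoint of the safety run-in cohorts. Under Section 3.1.1, up to 2 patients with a DLT opens the Phase 2 cohort at that dose, while 3 or more sends another 6 patients to a lower dose. In Cohort 2 the drug lowered is magrolimab, first from 30 to 20 mg/kg (Table 5).

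Section 1.8 plans safety assessments for all cohorts, "including monitoring for anemia, myelosuppression, tumor lysis syndrome (TLS), hepatotoxicity, IRRs, and other expected toxicities". Table 14 in Section 6.5.8 has phosphorus measured during the study in Cohorts 1 and 2. Section 5.2.3 lists phosphorus among the chemistries to watch for tumor lysis but does not say in which direction.

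**The concern.** Lysing cells release their contents, so phosphate rises along with potassium and uric acid. The entry names two elevations and, between them, a decrease. The term that belongs there is missing and the term that stands there does not fit. The three terms in parentheses are not marked as examples, so they read as a complete list.

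The list decides who counts as having a DLT, which is a primary endpoint and the input to the dose rule. A wrong term can move a patient across that line in either direction: high phosphate from tumor lysis can be counted when its companions are not, and low phosphate can be excused for 14 days on a ground that does not apply to it.

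**Working it through.** The plan has no figure to reproduce here; the check applies the wording case by case. In every row the event is Grade 3 or 4, treatment-related and worsened from baseline. "Grade 3 or 4 TLS or related electrolyte disturbances (hyperkalemia, hypophosphatemia, hyperuricemia) that resolve to ≤ Grade 2 within 14 days" is read with its electrolyte disturbances having to be related to TLS. The last column puts hyperphosphatemia in place of hypophosphatemia and changes nothing else.

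| Event | As written | Corrected word |
|---|---|---|
| Diagnosed TLS, resolved within 14 days | exempt | exempt |
| High potassium or uric acid attributed to tumor lysis, no TLS diagnosis, resolved in 8 to 14 days | exempt | exempt |
| Isolated Grade 3 high phosphate without consequences, resolved within 7 days | exempt | exempt |
| **High phosphate attributed to tumor lysis, no TLS diagnosis, resolved in 8 to 14 days** | **DLT** | **exempt** |
| **High phosphate attributed to tumor lysis, no TLS diagnosis, resolved within 7 days but meeting neither 7-day entry (for example Grade 4 with a clinical correlate)** | **DLT** | **exempt** |
| High phosphate not attributed to tumor lysis, resolved in 8 to 14 days | DLT | DLT |
| High phosphate lasting more than 14 days, no TLS diagnosis | DLT | DLT |
| **Low phosphate labelled TLS-related, resolved in 8 to 14 days** | **exempt** | **DLT** |

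Only the three rows in bold change. The first two count too much and the third counts too little.

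**Reach into the dose rule.** The threshold is 3 of 6. One patient wrongly counted, with no other DLT, changes the decision only if exactly 2 others have a DLT (2 + 1 = 3). With 0 or 1 others the total stays at 1 or 2 and Phase 2 opens anyway; with 3 or more others the dose is lowered anyway.

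**Cohorts.** Section 3.1.3 closes Cohort 1 after 7 run-in and 11 Phase 2 patients, and closes Cohort 3 with none enrolled. No dose decision remains in either. Cohort 2 is the only cohort whose run-in decision could still be affected, and the protocol does not say whether that decision has been made. DLT incidence is still to be reported for run-in patients, including the 7 in Cohort 1, who received venetoclax, for which Section 5.2.3 warns of TLS.

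**The case against.** The best defense is that the slip hardly matters. An investigator who sees high phosphate from tumor lysis can diagnose TLS, which is exempt under either wording, or can read the term as the obvious slip it is. The sponsor sets the Phase 2 dose on all relevant clinical and PK data (Section 3.1.1.2), and a safety review team assesses safety (Section 3.1.1.3). All of this stands and keeps the point small. It does not change the written definition, on which the endpoint rests.

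The intended word also cannot be proved from the protocol. The term appears once, the synopsis does not repeat the list, and no other section gives the direction. The inference rests on basic medical knowledge and on the two neighboring terms; it is strong, but it is an inference.

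Three stronger readings are tempting and are not supported:

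- *That the wrong word turns all treatment-related high phosphate of 8 to 14 days into DLTs.* The entry covers only TLS and disturbances related to it. High phosphate with another cause is a DLT with or without the correction.
- *That a dose decision has been, or probably will be, distorted.* The protocol gives no rate for such events. The spacing of chemistry visits does not supply a size either, since it applies equally to any laboratory abnormality and extra draws can be taken.
- *That the same list contradicts itself on nausea, vomiting and diarrhea*, which appear under both a 7-day and a 72-hour limit. The entries are alternative exceptions, so meeting either is enough. The 72-hour clock starts when medical management starts, so that entry can exempt an event the 7-day entry does not, and removing the three terms could narrow the exemption.

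**Conclusion.** Wrong as written, and minor. The entry names hypophosphatemia where hyperphosphatemia is evidently meant. The literal text misclassifies high phosphate that is attributed to tumor lysis but not diagnosed as TLS, lies outside both 7-day laboratory exceptions and resolves within 14 days. It also gives low phosphate labelled TLS-related a 14-day allowance it should not have.

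The effect is confined to any open Cohort 2 run-in decision and to DLT classification in run-in patients. No power, sample size or error rate in the protocol changes.

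The conclusion assumes that the parenthetical list is complete and that its disturbances must be related to TLS. If the list were read as illustrative, high phosphate would already be covered and only the wrong example would remain to correct.

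**What to change.** In the tumor lysis entry of Section 3.1.1.2, replace hypophosphatemia with hyperphosphatemia. Leave the nausea, vomiting and diarrhea entries as they are.

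The edit is one word and needs no new data. It is still a protocol modification that needs IRB/IEC approval before use (Section 9.1.3), so it is best carried in the next amendment.
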